#### **4.0 REGISTRATION PROCEDURES**

---

Subjects will be evaluated for eligibility by the site principal investigator to ensure that the inclusion and exclusion criteria have been met.

##### **4.1 Patient Registration Procedures**

Patients that have signed informed consent to participate in a UCHMC protocol must be registered with the initiating site and enrolled on the protocol.

Patients must be entered into the OnCore system the same day the informed consent is signed.

All patients will be assigned a specific study ID which will correlate with the study number, site number and patient enrollment numbers. Patient ID's will be assigned by the lead site and formatted as follows: UCHMC1913-XX-XX.

Study specific ID will be provided by the initiating site once eligibility is confirmed by the initiating center.

All patients must obtain a study ID number from the initiating center before initiation of treatment.

##### **4.2 Patient Eligibility**

Eligibility of the patient is determined by the clinical protocol and confirmed prior to registration. Participating sites need to send a redacted copy of the eligibility checklist signed by the treating investigator and accompanying redacted source which may include but is not limited to, pathology report, physical exam including ECOG, medical and oncology history and screening labs, must be provided to the initiating site for the specific study. Approval by initiating site PI and the initiating site clinical research manager is required prior to initiating treatment. Participating sites should send the requested redacted information above to [[contact]](mailto:[contact]) for confirmation of eligibility at least 3 business days prior to the planned start date of treatment.

#### **5.0 TREATMENT PLAN**

---

### 5.1 Treatment Dosage and Administration

Agent	Dose	Route	Schedule
CPX-351 for Induction	Daunorubicin 44mg/m  -cytarabine 100mg/m 	IV infusion for 90 minutes	Days 1, 3 and 5
CPX-351 for Reinduction	Daunorubicin 44mg/m  -cytarabine 100mg/m 	IV infusion for 90 minutes	Days 1 and 3
CPX-351 for Consolidation	Daunorubicin 29mg/m  -cytarabine 65mg/m 	IV infusion for 90 minutes	Days 1 and 3
Glasdegib	100 mg	PO daily in the a.m.	Begins day after completion of CPX-351 infusion and continues daily until Day 1 of subsequent cycle of CPX-351

### 5.2 Induction

During induction, patients will receive the combination of Glasdegib and CPX-351. The dose of Glasdegib is 100mg orally daily on days 6 to 28. CPX-351 will be given at a dose of daunorubicin 44mg/m^2-cytarabine 100mg/m^2 via 90 minute infusion on days 1, 3, 5. Induction can last longer than 28 days and up to 60 days. If induction last more than 28 days, patient should continue to take glasdegib daily and as prescribed until day 1 of next cycle of CPX-351. Patient will be instructed to hold glasdegib on the day they receive CPX-351 infusion..

### 5.3 Reinduction

Patients who are responding to the initial induction but not yet less than 5% blasts can receive a second induction. Patients who have not had any reduction in blasts count should be considered as refractory and should be considered for other treatment options off protocol. However, if there is a greater than 50% reduction in blast count but greater than 5% blasts present on marrow, re-induction is strongly recommended. The use of re-induction will be at the treating physician's discretion based on bone marrow biopsy performed on day 20 (+1 day). The regimen for re-induction will be CPX-351 at a dose of daunorubicin 44mg/m^2-cytarabine 100mg/m^2 on days 1 and 3. Glasdegib will be administered at 100mg daily on days 4-28. Reinduction can last longer than 28 days and up to 60 days. If reinduction last more than 28 days, patient should continue to take glasdegib daily and as prescribed until day 1 of next cycle of CPX-351. Patient will be instructed to hold glasdegib on the day they receive CPX-351 infusion.

### 5.4 Consolidation

Patients who achieve CR or CRi, can be continued on consolidation therapy for up to two cycles. In general, patients who have achieve CRi, consolidation should be initiated once the platelet count  $\geq$  50,000/uL and ANC  $\geq$  500/uL. The first consolidation cycle should start between 28 to 75 days after initiation of the last induction therapy. Each subsequent cycle of consolidation should be initiated between 28 to 55 days after the start of previous cycle of

consolidation. The exact day is at the treating physician's discretion. The number of consolidation cycles will depend on the time required for identification and availability of a suitable stem cell donor for patients going to stem cell transplantation.

The dose of CPX-351 will be at a dose of daunorubicin 29 mg/m^2–cytarabine 65 mg/m^2 on days 1 and 3. Glasdegib will be administered at 100mg daily for days 4-28. Consolidation cycles can last longer than 28 days. If cycles last more than 28 days, patient should continue to take glasdegib daily and as prescribed until day 1 of next cycle of CPX-351. Patient will be instructed to hold glasdegib on the day they receive CPX-351 infusion.

### **5.6 Allogenic stem cell transplantation**

The decision to go to allogeneic transplant once the patient is in remission is based on the treating's physician discretion as well as the desire of the patient. Patients who are considered candidates for allogeneic transplant and have a donor stem cell source available can proceed to allogeneic transplant. Alternatively, patients can receive up to two cycles of consolidation chemotherapy prior to allogeneic transplant.

For patients going to transplant, Glasdegib will be discontinued within 7 days prior to start of conditioning for their transplant.

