**STUDY SCHEMA**

\*Treatment will be discontinued for induction failure, relapsed or progressed disease, treatment intolerance, continuation to HSCT or at any point based on the investigator's discretion. At discontinuation, subjects will enter the follow-up portion of the study.

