	
 
9. History of GI malabsorptive disease
 
10. Has a known additional malignancy that is progressing or requires active treatment. Exceptions include basal cell carcinoma of the skin, squamous cell carcinoma of the skin, or in situ cervical cancer that has undergone potentially curative therapy
 
11. Known HIV infection
 
12. Active hepatitis B or hepatitis C infection (patients who successfully completed curative hepatitis C therapy can be enrolled)
 
13. Any uncontrolled infection, active bacterial or viral infection manifesting as fevers or hemodynamic instability within the past 72 hours
 
14. Proven active invasive fungal infection
 
15. Is pregnant or breastfeeding, or expecting to conceive or father children within the projected duration of the trial, starting with the pre-screening or screening visit through 120 days after the last dose of trial treatment
 
16. Severe or uncontrolled medical disorder that would, in the investigator’s opinion, impair ability to receive study treatment (i.e., uncontrolled diabetes, chronic renal disease, chronic pulmonary disease or active, uncontrolled infection, psychiatric illness/social situations that would limit compliance with study requirements
 
17. Current or anticipated use of other investigational agents
 
18. For patients with prior anthracycline exposure, the cumulative life-time dose should not exceed 386mg/m^2 at the time of study entry (to convert different anthracycline to daunorubicin-equivalent, see Appendix H for conversion factors)
 

Study Product(s)	CPX-351 and Glasdegib
Duration of administration	
 
• CPX-351 will be administer during Induction on days 1, 3 and 5. Glasdegib will be given starting on day 6 and continuing until beginning of consolidation
 
• Consolidation can be either 1 or 2 cycles. CPX-351 will be administered during days 1 and 3. Glasdegib will begin on day 4 and continue daily
 
• If the patient is a candidate for HSCT and moves forward with HSCT, then Glasdegib will be discontinued at least 7 days prior
 

	
 
• During Maintenance, Glasdegib will be taken daily for up to 1 year
 

Reference therapy	Lancet Phase II CPX-351 versus 7+3. Blood 2014

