**Footnotes:**

- A Must be obtained before undergoing any protocol-specific study procedures, unless as part of standard of care
- B Serum beta-HCG should be done for any female of child-bearing potential
- C Bone marrow collections do not need to be repeated if a diagnostic bone marrow procedure was done prior to informed consent and is done within 28 days of starting day 1 of induction
- D Collect bone marrow aspirate for research sample for gene expression correlatives; if patient has any circulating blasts, then peripheral blood can be collected instead of aspirate; if bone marrow is a “dry tap,” then this sample does not need to be collected
- E Re-induction is based on response evaluation bone marrow done on day 20 of induction. If there is greater than 5% blast count, re-induction is recommended. The final decision for re-induction is based on investigator’s discretion. For patients who will be treated with re-induction, an ECHO and pregnancy test (for female patients of child-bearing potentials) will be done before starting re-induction
- F Omit CPX-351 on day 5 for participants receiving re-induction

G ECG is done pre-dose and can be done up to 24 hours before planned glasdegib dosing

H During induction, repeat an ECG a week after starting glasdegib (around day 13-15). If clinically significant abnormal ECG or clinically significant changes in QTc, then refer to section 6.4 for further guidance. If normal or non-clinically significant abnormalities and/or changes in QTc, additional ECG monitoring is not required and is done per the treating investigator's discretion

I Glasdegib should continue until day 1 of the next cycle of CPX-351

J Up to two cycles of consolidation is allowed. These are 28 day cycles, unless delays are necessary. In the case of a delay, glasdegib will continue daily until the start of CPX-351 infusion in the next cycle. If the patient will proceed to allogenic SCT, then consolidation can be skipped or shorten. Glasdegib will be stopped at least 7 days before transplant.

K These are 28 days cycle. Patients who are not receiving HSCT will be allowed to proceed to glasdegib maintenance for up to 1 year of study start

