### **5.8 Duration of Therapy**

In the absence of treatment delays due to adverse events, treatment may continue until completion or protocol-defined therapy or until:

- Disease progression
- Inter-current illness that prevents further administration of therapy
- Unacceptable adverse events
- Patient decided to withdraw from the study
- General or specific examples in the patient's condition render the patient unacceptable for further treatment in the judgement of the investigator

Subjects who become medically incapacitated or cognitively impaired after enrollment into this trial may continue with protocol therapy as long as they are benefiting from treatment in the judgement of the investigator. In the event that this occurs, a surrogate or legally authorized representative (LAR) must sign the ICF. The surrogate/LAR will assist the subject in completion of study procedures and diary. If a subject regains ability to regains the cognitive ability to consent, they must be re-consented using standard consenting procedure

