#### **8.0 Removal of Subjects from Study Treatment and Study**

---

Patients can be taken off the study treatment and/or study at any time at their own request, or they may be withdrawn at the discretion of the investigator for safety, behavioral or administrative reasons. The reason(s) for discontinuation will be documented and may include:

1. Patient completed study treatment;
2. Patient voluntarily withdraws from treatment (follow-up permitted);
3. Patient withdraws consent (termination of treatment and follow-up);
4. Patient/LAR is unable to comply with protocol requirements;
5. Patient demonstrates disease progression (unless continued treatment with study drug is deemed appropriate at the discretion of the investigator);
6. Patient experiences toxicity that makes continuation in the protocol unsafe;

7. Treating physician judges continuation on the study would not be in the patient's best interest;
8. Patient becomes pregnant (pregnancy to be reported along same timelines as a serious adverse event);
9. Development of second malignancy (except for basal cell carcinoma or squamous cell carcinoma of the skin) that requires treatment, which would interfere with this study;
10. Lost to follow-up.

If a research subject cannot be located to document survival after a period of 2 years, the subject may be considered "lost to follow-up." All attempts to contact the subject during the two years must be documented.

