  1. Unexpected (in term nature, severity, or frequency) given the following: a) the research procedures described in the protocol-related documents such as the IRB approved research protocol, informed consent document or Investigator Brochure (IB); and b) the characteristics of the subject population being studied; AND
  2. Related or possibly related to participation in the research (possibly related means there is a reasonable possibility that the incident, experience, or outcomes may have been caused by the drugs, devices or procedures involved in the research); AND
  3. Suggests that the research places subjects or others at greater risk of harm (including physical, psychological, economic, or social harm) than previously known or recognized.
- **Protocol Violation**- A protocol violation is an accidental or unintentional change to or noncompliance with the IRB-approved protocol that increases risk or decreases benefit and/or affects the subject's rights, safety, welfare, and/or the integrity of the data.

Examples of incidents that may be considered violations include: enrolling a participant who does not meet the inclusion criteria; obtaining verbal consent before the initiation of study procedures when the IRB requires signed, written informed consent; and failure to collect screening labs before initiation of study procedures [Reference: Policy #57 UCI HRPP Policy and Procedure Glossary].

- **Protocol Deviation-** a protocol deviation is an accidental or unintentional change to the research protocol that does not increase risk or decrease benefit or have a significant effect on the participant's rights, safety or welfare, or on the integrity of the data. Deviations may result from the action of the participant, researcher, or staff. Examples: a rescheduled study visit, an omitted routine safety lab for a participant with previously normal values; or failure to collect an ancillary self-report questionnaire data (e.g., quality of life) [Reference: Policy #57 UCI HRPP Policy and Procedure Glossary].

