#### **14.5.18 Protocol Violations**

Any unplanned variance from an IRB approved protocol is considered a violation and must be reported to the IRB in a timely fashion.

- A.** All major protocol deviations will be reported in accordance with UCI IRB, UCI CFCCC Stern Center policies, UCI DSMB and the participating site's IRB policies.

Major violations include:

- Instances that have harmed or increased the risk of harm to one or more research participants.
- Instances that have damaged the scientific integrity of the data collected for the study.
- Results from willful or knowing misconduct on the part of the investigator(s).
- Demonstrates serious or continuing noncompliance with federal regulations, State laws, or University policies.

- B.** Minor violations may be reported to the IRB at the time of the continuing review.

Minor violations have no substantive effect on the risks to participants or on the scientific integrity of the research plan or the value of the data collected.

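### Section 5.6 sets no minimum gap between the last glasdegib dose and transplant, so a stop that it allows can miss the 7-day minimum in Schedule of Events footnote J

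*Combined protocol and SAP*

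**What the plan says.** Three places time the last glasdegib dose for a patient going to transplant.

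- Section 5.6: "Glasdegib will be discontinued within 7 days prior to start of conditioning for their transplant".
- Schedule of Events, footnote J: "Glasdegib will be stopped at least 7 days before transplant".
- Study Summary, Duration of administration: "If the patient is a candidate for HSCT and moves forward with HSCT, then Glasdegib will be discontinued at least 7 days prior". The sentence ends there. HSCT is the only antecedent, and no reference date is written.

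Otherwise glasdegib is taken daily until day 1 of the next CPX-351 cycle (Sections 5.1 and 5.4). A patient leaving for transplant has no next cycle, so the transplant rule decides the last dose.

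Other provisions allow treatment to stop without timing that dose. The Study Schema lists "continuation to HSCT or at any point based on" the investigator's discretion among the grounds for stopping. Section 5.8 allows a stop when changes in the patient's "condition render the patient unacceptable for further treatment in the judgement of the investigator". Section 8.0 says of patients that "they may be withdrawn at the discretion of the investigator for safety, behavioral or administrative reasons".

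**The concern.** The three texts differ in direction and in reference date. Section 5.6 says *within* 7 days and counts from the start of conditioning. Footnote J says *at least* 7 days and counts from transplant. The Summary says *at least* 7 days and leaves the date unstated. No section says which prevails.

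Read literally, Section 5.6 lets a site dose until conditioning starts. If conditioning is short, the gap to transplant is then less than the minimum set in footnote J. Up to five centers could apply different stop rules, and the same last dose could comply with one section and breach another. What is at stake is consistent dosing, washout length and the classification of deviations in transplanted patients.

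**Working it through.** There is no stated figure in the plan to reproduce. The check is day arithmetic.

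**Inputs**
- s = days from last glasdegib dose to start of conditioning. Section 5.6 allows s = 0 to 7 (8 whole days), or s = 1 to 7 (7 days) if a same-day stop is excluded.
- c = days from start of conditioning to transplant. This is not in the documents, so it is assumed and shown as a range.
- Footnote J requires s + c ≥ 7.

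**Formulas**
- An allowed stop misses footnote J when s < 7 − c.
- Number of allowed days that miss it: max(0, 7 − c) of 8 when s starts at 0; max(0, 6 − c) of 7 when s starts at 1.
- Shortest gap to transplant under Section 5.6: c days (s = 0) or c + 1 days (s = 1).

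| c (assumed) | Miss, s = 0 to 7 | Miss, s = 1 to 7 | Shortest gap, days (s = 0 / s = 1) |
|---|---|---|---|
| 2 | 5 of 8 | 4 of 7 | 2 / 3 |
| 3 | 4 of 8 | 3 of 7 | 3 / 4 |
| 4 | 3 of 8 | 2 of 7 | 4 / 5 |
| 5 | 2 of 8 | 1 of 7 | 5 / 6 |
| 6 | 1 of 8 | 0 of 7 | 6 / 7 |
| 7 | 0 of 8 | 0 of 7 | 7 / 8 |

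Example: at c = 3, a last dose on the day conditioning starts gives 0 + 3 = 3 days, against 7 required.

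**Summary rule.** If its unstated date is transplant, the table applies unchanged. If it is the start of conditioning, the rule is s ≥ 7. Every stop with s < 7 then misses it at any c: 7 of the 8 allowed days, or 6 of 7.

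**A date that meets everything.** At s = 7, Section 5.6 is met, s + c = 7 + c ≥ 7 meets footnote J, and s ≥ 7 meets the Summary on either reading.

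**Who the rule could reach.** Section 1.5.3 gives a 34% transplant rate on CPX-351 in the phase III trial. Applied to 30 patients, 0.34 × 30 = 10.2, or about 10 (95% binomial range 5 to 15). That trial enrolled ages 60 to 75, while this one enrolls from 18, and the rule matters only for patients still taking glasdegib. The figure counts patients who may be exposed to the rule, not late stops. The documents do not allow late stops to be counted.

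**The case against.** The strongest reply is that the rules are compatible. A protocol is read as a whole, and a stop exactly 7 days before conditioning satisfies all three texts. A late stop needs a site to follow Section 5.6 alone, use the last days of its window and give short conditioning. The counts above are calendar options, not a rate, and they vanish at c of 7 or more. All of that stands, and it is why the claim is that a Section 5.6 stop *can* miss the minimum. It does not remove the defect: a site following the treatment section as written has no warning that a later stop breaks footnote J.

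The Summary is also weaker support than it looks. It falls at a table break in the copy read, so a reference date may have been lost. The counts that depend on c are therefore firm only against footnote J.

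Four stronger readings are tempting, and the documents support none of them.

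- *The rules exclude each other, so stopping earlier than the Section 5.6 window is itself a breach.* They share at least one date, and the Study Schema and Sections 5.8 and 8.0 allow earlier stopping on the investigator's judgement.
- *A late stop harms patients.* No reason for the 7 days is given, so no specific toxicity can be claimed.
- *A late stop is trivial.* Section 11.1 says that "a protocol deviation is an accidental or unintentional change to the research protocol that does not increase risk or decrease benefit", and Section 14.5.18 says that "Minor violations may be reported to the IRB at the time of the continuing review". But the table in Section 11.4 gives a wrong drug dosage as an example of a violation, due at the coordinating center within 24 hours. The classification is not settled either way.
- *The primary result is affected.* The EFS6 rule in Section 13.2.3 does not use the glasdegib stop date.

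**Conclusion.** The inconsistency is real and minor. Section 5.6 sets no minimum washout, while footnote J sets one of 7 days before transplant, so a stop that Section 5.6 permits can fall short when conditioning starts fewer than 7 days before transplant (fewer than 6 if a same-day stop is excluded). Confidence is high for the wording conflict and the day counts against footnote J. The practical effect is uncertain: it rests on an assumed conditioning length and on how sites read Section 5.6. If the Summary meant conditioning, the conflict with it holds at any conditioning length. No effect on alpha, power, sample size or EFS6 is shown.

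**What to change.** In Section 5.6, replace the window before conditioning with a stop *at least 7 days before transplant*. Complete the Study Summary sentence with the same reference date. Footnote J stays as it is, and all three places then agree. Until the amendment is approved, tell sites that the footnote J minimum governs the last dose. That applies existing text.

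The cost is wording in two places. A patient who would otherwise dose until conditioning loses at most max(0, 7 − c) glasdegib days: 5 at c = 2, 4 at c = 3, none at c of 7 or more. No statistical rework is needed.

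Anchoring instead at 7 days or more before conditioning would also meet footnote J at every c. It would lengthen the minimum gap to transplant to 7 + c days (9 at c = 2, 13 at c = 6) and remove up to 7 dosing days, or 6 if a same-day stop is excluded. Footnote J does not ask for that longer gap. It is an optional clinical choice and is not needed to correct the error.

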### **5.7 Maintenance**

For patients who complete consolidation chemotherapy and not proceeding to allogeneic transplant, they will proceed to maintenance therapy. Glasdegib oral daily will be continued for up to one year. The patients will proceed with monthly assessments of disease status if they are on Glasdegib maintenance. If they are adults of child-bearing age and potential, they will need to be reminded of contraception. If they are a woman of child-bearing age and potential, they will need to have pregnancy test.

